9 SAFETY ASSESSMENTS

9.1 Adverse Events

An adverse event is defined as any untoward medical occurrence in a patient or clinical investigation subject administered a pharmaceutical product, which does not necessarily have a causal relationship with this treatment. An adverse event can therefore be any unfavorable and/or unintended sign (including an abnormal laboratory finding), symptom, or disease temporally associated with the use of study drug, whether or not related to the study drug. All adverse events, including observed or volunteered problems, complaints, or symptoms, are to be recorded on the appropriate eCRF.

Adverse events, which include clinical laboratory test variables, will be monitored and documented from the time the subject signs consent through the Follow Up Visit. Subjects should be instructed to report any adverse event that they experience to the Investigator, whether or not they think the event is due to study drug. Beginning at Screening (following completion of an Informed Consent Form by the subject), Investigators should make an assessment for adverse events at each visit and record the event on the appropriate adverse event eCRF.

Wherever possible, a specific disease or syndrome rather than individual associated signs and symptoms should be identified by the Investigator and recorded on the eCRF. However, if an observed or reported sign or symptom is not considered a component of a specific disease or syndrome by the Investigator, it should be recorded as a separate adverse event on the eCRF. Additionally, the condition that led to a medical or surgical procedure (e.g., surgery, endoscopy, tooth extraction, or transfusion) should be recorded as an adverse event, not the procedure itself.

Any medical condition already present at consent should be recorded as medical history and not be reported as an adverse event unless the medical condition or signs or symptoms present at Baseline changes in severity, frequency, or seriousness at any time during the study. In this case, it should be reported as an adverse event.

Subjects who develop treatment-related SAEs, treatment-related Grade 3 or higher AEs, or clinically significant treatment-related Grade 3 or higher laboratory abnormalities should be followed until resolution of the AE or laboratory abnormality, or, if the AE or laboratory abnormality was present at baseline, until the value returns to baseline level.

Clinically significant abnormal laboratory or other examination (e.g., ECG) findings that are detected during the study or are present at initial dosing and significantly worsen during the study should be reported as adverse events, as described below. The Investigator will exercise his or her medical and scientific judgment in deciding whether an abnormal laboratory finding or other abnormal assessment is clinically significant. Clinically significant abnormal laboratory values occurring during the clinical study will be followed until repeat tests return to normal, stabilize, or are no longer clinically significant. Abnormal test results that are determined to be an error should not be reported as an adverse event. Laboratory abnormalities or other abnormal clinical findings (e.g., ECG abnormalities) should be reported as an adverse event if any of the following are applicable:

- If an intervention is required as a result of the abnormality
- If action taken with the study drug is required as a result of the abnormality
- Based on the clinical judgment of the Investigator

9.1.1 Adverse (Drug) Reaction

All noxious and unintended responses to a study drug related to any dose should be considered an adverse drug reaction. “Responses” to a study drug means that a causal relationship between a study drug and an adverse event is at least a reasonable possibility, i.e., the relationship cannot be ruled out.

9.1.2 Unexpected Adverse Drug Reaction

An Unexpected Adverse Drug Reaction is defined as an adverse reaction, the nature or severity of which is not consistent with the applicable product information. For MAU868 the reference safety information is included in the IB currently in force. The reference safety information will be reviewed yearly, and the periodicity of the review will be harmonized with the reporting period of the Development Safety Update Report.

9.1.3 Assessment of Adverse Events by the Investigator

The Investigator will assess the severity (intensity) of each adverse event and will also categorize each adverse event as to its potential relationship to study drug using the categories of “yes” or “no.”

Assessment of Severity

The severity of all adverse events should be graded according to the CTCAE v5.0. For those adverse event terms not listed in the CTCAE, the following grading system should be used:

- CTCAE Grade 1: Mild; asymptomatic or mild symptoms; clinical or diagnostic observations only; intervention not indicated
- CTCAE Grade 2: Moderate; minimal local or noninvasive intervention indicated; limiting age-appropriate instrumental activities of daily living
- CTCAE Grade 3: Severe or medically significant but not immediately life-threatening; hospitalization or prolongation of hospitalization indicated; disabling; limiting self-care activities of daily living
- CTCAE Grade 4: Life threatening consequences; urgent intervention indicated

CTCAE Grade 5: Death related to the adverse event

Causality Assessment

The relationship of an adverse event to the administration of the study drug is to be assessed according to the following definitions:

No (not related, unlikely to be related) – The time course between the administration of study drug and the occurrence or worsening of the adverse event rules out a causal relationship and another cause (concomitant drugs, therapies, complications, etc) is suspected.

Yes (possibly, probably, or definitely related) – The time course between the administration of study drug and the occurrence or worsening of the adverse event is consistent with a causal relationship and no other cause (concomitant drugs, therapies, complications, etc) can be identified.

The definition implies a reasonable possibility of a causal relationship between the event and the study drug. This means that there are facts (evidence) or arguments to suggest a causal relationship.

The following factors should also be considered:

- The temporal sequence from study drug administration
The event should occur after the study drug is given. The length of time from study drug exposure to event should be evaluated in the clinical context of the event.
- Underlying, concomitant, intercurrent diseases
Each report should be evaluated in the context of the natural history and course of the disease being treated and any other disease the subject may have.
- Concomitant drug
The other drugs the subject is taking or the treatment the subject receives should be examined to determine whether any of them might be recognized to cause the event in question.
- Known response pattern for this class of study drug.
Clinical and/or preclinical data may indicate whether a particular response is likely to be a class effect.
- Exposure to physical and/or mental stresses
The exposure to stress might induce adverse changes in the recipient and provide a logical and better explanation for the event.
- The pharmacology and PK of the study drug.
The known pharmacologic properties (absorption, distribution, metabolism, and excretion) of the study drug should be considered.

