3.3 Discontinuation Rules

3.3.1 Study Stopping Rules

The study may be discontinued or paused for reasons that may include (but are not limited to): reasons of safety, lack of study drug availability, inability to enroll the study, or decision by a regulatory authority or the Sponsor (see [Appendix D](#)).

In the event that a dosing cohort shows efficacy and it is not anticipated that additional dosing would show added efficacy, the Sponsor may choose to stop and not complete the study.

Further, in the instance of 2 or more treatment-related SAEs, 2 or more treatment-related AEs Grade 3 or higher or 2 or more clinically significant treatment-related Grade 3 or higher laboratory abnormalities, the study will be paused pending an SSRC review of the safety events. The Sponsor will inform the applicable regulatory authorities of any safety-related pause in the study.

In the case that the study is discontinued, the Sponsor will promptly inform the Investigators and applicable regulatory authority(ies) of the termination of the study and the reason(s) for the termination. The Investigators are responsible for promptly informing subjects that they must discontinue study drug. The Institutional Review Board (IRB)/Independent Ethics Committee (IEC) will also be informed promptly and provided the reason(s) for the termination, as specified by the applicable regulatory requirement(s).

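### The Yes/No causality definitions in Protocol 9.1.3 leave some adverse events unclassifiable and disagree with 9.1.1, so the relatedness call that feeds the study pause is indeterminate

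*Protocol*

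**What the plan says.** Protocol 9.1.3 asks the investigator for a two-way relatedness call, with no third or unknown category. Each answer carries two conditions joined by *and*:

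- **Yes**, labelled as covering possibly, probably and definitely related events: the time course "is consistent with a causal relationship and no other cause (concomitant drugs, therapies, complications, etc) can be identified".
- **No**, labelled as covering unrelated and unlikely related events: the time course "rules out a causal relationship and another cause (concomitant drugs, therapies, complications, etc) is suspected".

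The same section then adds: "The definition implies a reasonable possibility of a causal relationship between the event and the study drug". It goes on to list factors to consider, among them underlying disease and other drugs.

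Protocol 9.1.1 defines an adverse drug reaction by a different test, namely that "a causal relationship between a study drug and an adverse event is at least a reasonable possibility, i.e., the relationship cannot be ruled out".

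Protocol 3.3.1 pauses the study "in the instance of 2 or more treatment-related SAEs", or on the same count of treatment-related Grade 3 or higher AEs or clinically significant laboratory abnormalities. Section 3.3.2 makes individual discontinuation mandatory for one such event. SAP 7.4.1 tabulates study drug-related TEAEs and serious TEAEs without defining the term.

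**The concern.** Under 9.1.3, Yes requires that no competing explanation can be found, while 9.1.1 asks only whether the drug can be excluded. These are different standards for the same judgement. Under 9.1.3 a competing explanation defeats Yes even where the drug remains a plausible cause.

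In this population the case is easy to picture. Protocol 1.8 lists renal dysfunction among the potential risks of MAU868. Every subject has a kidney graft and BK viremia, and Protocol 1.1 describes BKV nephropathy, and rejection after immunosuppression is reduced, as recognised outcomes. A renal event after an infusion could have all of these as candidate causes.

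With a pause count of only two, each classification carries weight. Planned enrolment is about 36 subjects at about 20 sites, or 36 / 20 = 1.8 subjects per site. Most investigators would therefore settle the ambiguity on very few cases, with little chance to develop a consistent local practice.

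**Working it through.** **Step 1. Apply each definition to every combination of its conditions.** The inputs are the two conditions in 9.1.3 and the standard in 9.1.1.

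| Time course | Other cause | 9.1.3 | 9.1.1 |
|---|---|---|---|
| Compatible | None identified | Yes | Reaction |
| Compatible | Identified | Neither | Reaction |
| Excludes causality | Suspected | No | Not a reaction |
| Excludes causality | None suspected | Neither | Not a reaction |

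Two of the four cells have no answer in 9.1.3. The fourth row is harmless, since 9.1.1 settles it. The second row is the problem: 9.1.1 calls the event a reaction, and 9.1.3 withholds both answers.

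**Step 2. Check 9.1.3 against itself.** The Yes label admits possibly related events, and the sentence after the definitions speaks of a reasonable possibility. Neither fits a requirement that every alternative be absent. The No label admits events unlikely to be related, yet its definition demands timing that excludes the drug.

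**Step 3. Trace what uses the call.** Sections 3.3.1 and 3.3.2 do not define *treatment-related*, and 9.1.3 is the only place where a relatedness category is assigned. I therefore take its Yes as the input to:

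- the two-event pause (3.3.1);
- the relatedness-based discontinuation criteria (3.3.2, repeated in 9.1.4, 9.2 and Appendix D);
- SAE reporting after the Follow Up Visit, which covers only events the investigator considers related (9.3.1);
- the drug-related TEAE and serious TEAE tables (SAP 7.4.1).

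**Step 4. Illustrate the sensitivity of the pause.** The plan states no event rate, so there is no figure to reproduce and both inputs are assumptions. Let p be the chance that a subject has an event of one trigger type that 9.1.1 would count, and g the share of those events with another identifiable cause that are coded No. Treat each of 36 subjects as contributing at most one event (the protocol counts events, so this is a simplification). With q = p(1 − g):

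P(at least 2) = 1 − (1 − q)^36 − 36q(1 − q)^35

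For p = 0.10 and g = 0, q = 0.10, and 1 − 0.0225 − 0.0901 = 0.887. For p = 0.10 and g = 0.50, q = 0.05, and 1 − 0.158 − 0.299 = 0.543.

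| p (assumed) | g = 0 | g = 0.25 | g = 0.50 | g = 0.75 |
|---|---|---|---|---|
| 0.05 | 0.543 | 0.393 | 0.227 | 0.074 |
| 0.10 | 0.887 | 0.763 | 0.543 | 0.227 |
| 0.20 | 0.997 | 0.979 | 0.887 | 0.543 |

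If investigators code all such events Yes, relying on the *possibly* label, the g = 0 column applies and nothing is lost. The table shows how far the pause depends on how the gap is filled. It does not predict how it will be filled.

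**The case against.** A reader might infer that related events will be under-counted. The documents do not show that. An event in the second row fails No as clearly as it fails Yes, and both the *possibly* label and the reasonable-possibility sentence support coding it Yes. This stands: what is established is indeterminacy, with under-counting as one possible result. The sentence does not cure the defect, however, because it leaves the condition about other causes in place.

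A reader might also infer that most adverse events in transplant recipients fall into the gap. That is plausible on clinical grounds, but the documents give no frequency for events with competing causes. The illustration does not supply one, since it assumes g.

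Third, the reach is limited, and this also stands:

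- The primary objective is assessed through all adverse events, vital signs, ECGs and laboratory data (Protocol 10.4). SAP 7.4.1 tabulates all TEAEs and all SAEs by treatment group, so the comparison with placebo needs no causality call.
- Expedited reporting (9.5) concerns suspected adverse *reactions*, which 9.1.1 defines on the broader standard. All SAEs from first dosing to the Follow Up Visit are reported within 24 hours whatever their cause (9.3.1).
- The DSMB reviews cumulative unblinded safety data and, under SAP section 4, may suspend enrolment at any time.
- Section 3.3.2 also allows discontinuation for an SAE or clinically significant AE on judgement, without a relatedness test, and 3.3.1 allows a pause for other safety reasons.

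These safeguards reduce the consequence. None of them makes the two-event count or the mandatory discontinuation criteria well defined.

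**Conclusion.** The point holds as an inconsistency in a stated rule. The two definitions in 9.1.3 are not exhaustive, and they conflict with the section's own label and with 9.1.1 for events that have compatible timing and another possible cause. The consequence is indeterminate classification, with a risk of inconsistent coding between sites and of under-counting under a literal reading of Yes. It is confined to the four uses in Step 3, and rests on reading *treatment-related* there as the 9.1.3 call.

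Its size cannot be derived from the documents. Under the assumed inputs above, coding half of the otherwise countable events No lowers the chance of reaching two from 0.887 to 0.543 at p = 0.10; coding them Yes leaves it unchanged. The stronger conclusions, that the safety tables as a whole, the primary objective or expedited reporting are compromised, are not supported. The inconsistency should be corrected because the remedy is cheap and the pause count is small.

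**What to change.** Reconcile 9.1.1 and 9.1.3 so that every event falls into exactly one category under the single reasonable-possibility standard the protocol already states in both sections. Yes would mean that a causal relationship is a reasonable possibility, whether or not another cause is also possible; No would mean that it is not. Another possible cause then becomes one of the listed factors to weigh and ceases to be a condition of Yes. State that *treatment-related* in 3.3.1 and 3.3.2 and *study drug-related* in SAP 7.4.1 both refer to this call. Leave the pause and discontinuation thresholds as they are.

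The direct cost is a protocol clarification, matching text in the eCRF completion guidelines and one sentence in the SAP. The operational cost should be acknowledged: some events may be newly classed as related, so pauses or discontinuations could be triggered somewhat more often. The documents give no figure for how many.

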9.1.4 AEs of Special Interest

For subjects experiencing infusion-associated AEs, the Investigator, or designee, is responsible for determining if immediate discontinuation of study therapy is required (see [Section 3.3.2](#)). In addition, for all cases of AEs associated with study infusion that occur during or within 2 hours after the completion of infusion require enhanced reporting using the specified Infusion-associated AE Report eCRF, regardless of whether drug discontinuation criteria are met.

Note: All treatment-related AEs of grade 3 or higher and treatment-related AEs of cytokine release syndrome and serum sickness of grade 2 or higher require discontinuation from study drug (see [Section 3.3.2](#)).

9.2 Serious Adverse Events

An adverse event or adverse reaction is considered serious if, in the view of either the Investigator or Sponsor, it results in any of the following outcomes:

- Death.

- A life-threatening adverse event.

Note: An adverse event or adverse reaction is considered “life-threatening” if, in view of either the Investigator or Sponsor, its occurrence places the subject at immediate risk of death. It does not include an event that, had it occurred in a more severe form, might have caused death.

- Requires hospitalization or prolongation of existing hospitalizations.

Note: Any hospital admission with at least one overnight stay will be considered an inpatient hospitalization. An emergency room or urgent care visit without hospital admission will not be recorded as a SAE under this criterion, nor will hospitalization for a procedure scheduled or planned before signing of informed consent, or elective treatment of a pre-existing condition that did not worsen from Baseline. However, unexpected complications and/or prolongation of hospitalization that occur during elective surgery should be recorded as adverse events and assessed for seriousness. Admission to the hospital for social or situational reasons (i.e., no place to stay, live too far away to come for hospital visits, respite care) will not be considered inpatient hospitalizations.

- A persistent or significant disability/incapacity or substantial disruption of the ability to conduct normal life functions.
- A congenital anomaly/birth defect.
- An important medical event.

Note: Important medical events that do not meet any of the above criteria may be considered an SAE when, based upon appropriate medical judgment, they may jeopardize the subject and may require medical or surgical intervention to prevent one of the outcomes listed above. Examples of such medical events include allergic bronchospasm requiring intensive treatment in an emergency room or at home, blood dyscrasias or convulsions that do not result in inpatient hospitalizations, or the development of drug dependency.

Note: All treatment related SAEs require discontinuation from study drug (see [Section 3.3.2](#))

9.3 Serious Adverse Event Reporting – Procedures for Investigators

9.3.1 Initial Reports

All SAEs occurring from the time of initial dosing until the Follow Up Visit must be reported to Medpace Clinical Safety within 24 hours of the knowledge of the occurrence (After the Follow Up Visit, any SAE that the Investigator considers related to study drug must be reported to the Medpace Clinical Safety or the Sponsor/designee).

To report the SAE, complete the SAE form electronically in the electronic data capture (EDC) system for the study. When the form is completed, Medpace Safety personnel will be notified electronically by the EDC system and will retrieve the form. If the event meets serious criteria and it is not possible to access the EDC system, send an email to Medpace Safety at [Medpace [contact]](mailto:[contact]) or call the Medpace SAE reporting line (phone number listed below), and fax/email the completed paper SAE form to Medpace (contact information listed in

Section 13.2 Address List) within 24 hours of awareness. When the EDC system becomes available, the SAE information must be entered within 24 hours of the system becoming available.

Safety Contact Information:

Medpace Clinical Safety

Medpace SAE reporting line – USA:

[contact], dial 3 or [contact], dial 3

[contact] or [contact]

Email: [contact]

9.3.2 Follow-up Reports

The Investigator must continue to follow the subject until the SAE has subsided or until the condition becomes chronic in nature, stabilizes (in the case of persistent impairment), or the subject dies.

Within 24 hours of receipt of follow-up information, the Investigator must update the SAE form electronically in the EDC system for the study and submit any supporting documentation (eg, patient discharge summary or autopsy reports) to Medpace Clinical Safety via fax or email. If it is not possible to access the EDC system, refer to the procedures outlined above for initial reporting of SAEs.

9.4 Pregnancy Reporting

If a subject becomes pregnant during the treatment period, the Investigator is to stop dosing with study drug immediately.

A pregnancy is not considered to be an adverse event or SAE; however, it must be reported to Medpace Clinical Safety within 24 hours of knowledge of the event. Medpace Clinical Safety will then provide the Investigator/site the Exposure In Utero (EIU) form for completion. The Investigator/site must complete the EIU form and fax/email it back to Medpace Clinical Safety.

If the female partner of a male subject becomes pregnant while the subject is receiving study drug or within the safety follow-up period defined in the protocol, the Investigator should notify Medpace Clinical Safety as described above.

The pregnancy should be followed until the outcome of the pregnancy, whenever possible. Once the outcome of the pregnancy is known, the EIU form should be completed and faxed/mailed to Medpace Clinical Safety. If the outcome of the pregnancy meets the criteria for immediate classification as an SAE (i.e., postpartum complication, spontaneous abortion, stillbirth, neonatal death, or congenital anomaly), the Investigator should follow the procedures for reporting an SAE.

9.5 Expedited Reporting

The Sponsor/designee will report all relevant information about Suspected Unexpected Serious Adverse Reactions (SUSAR) that are fatal or life-threatening as soon as possible to the Food and Drug Administration (FDA), Health Canada, and to the Central Ethics Committee, and in any case no later than 7 days after knowledge by the Sponsor/designee of such a case. Relevant follow-up information will subsequently be communicated within an additional 8 days.

All other SUSARs will be reported to the FDA, applicable competent authorities concerned, and to the Central Ethics Committee concerned as soon as possible but within a maximum of 15 days of first knowledge by the Sponsor/designee.

The Sponsor/designee will also report any additional expedited safety reports required in accordance with the timelines outlined in country-specific legislation.

The Sponsor/designee will also inform all Investigators as required per local regulation.

The requirements above refer to the requirements relating to Study MAU868-201.

